9.3 Statistics

Non-parametric or parametric statistics are used for LSR-scores, tumor size assessment and clearance rates. Descriptive data will be presented with medians and interquartile ranges (IQR) or means and standard deviations. Wilcoxon matched-pairs test will be used to test differences between test areas at various time points. P-values will be corrected for multiple comparisons when relevant and a level of $p<0.05$ considered statistically significant. Analyses are performed by SPSS version 24 (IBM Corporation, Armonk, NY, USA).

10. Quality Control, Data Protection & Storage

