3.4 Summary of Outcome Measures and Methods

Outcome measures and methods/techniques are summarized below. Detailed descriptions are presented in Section 6 and Table 1 (Appendix 1).

Primary outcome:

To investigate tolerability of topical AFL-assisted cisplatin+5-FU therapy for BCC by evaluating:

- I. Severity and duration of clinical local skin reactions including erythema, edema, scabbing, flaking and pustulation assessed by a physician using an established 0-4 point scale (none, mild, moderate, severe) from 0-30 days post-treatment.

- II. Occurrence of side effects (prolonged erythema/edema, hyper/hypopigmentation, scarring and infection) up to 3 months post-treatment.

Secondary outcome:

- 1) To monitor BCC tumor size and clearance based on clinical assessments and dermoscopy, supported by non-invasive imaging techniques including dynamic optical coherence tomography (D-OCT), reflectance confocal microscopy (RCM), high intensity focused ultrasound (HIFU) and histological analysis up to 3 months post-treatment.

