3.5 Preliminary Study

In the beginning of the trial period, a preliminary study in 4-6 patients of the intended treatment will be conducted to confirm: a) uniform cisplatin and 5-FU uptake in treated BCC tumors and b) no clinically relevant systemic drug uptake. Thus, up to 6 patients will each provide a single 4 mm punch biopsy of a treated BCC and one 5 ml blood sample, both taken 24 hrs after AFL-assisted cisplatin+5-FU. Drug biodistribution imaging of tumor sections and drug quantification in blood will be performed at Copenhagen University using well-established analytical techniques. A biobank and contracts of collaboration pertaining to the exchange of anonymized data between institutions will be devised.

4. Participants

Up to 12 patients with superficial BCC and 12 patients with nodular BCC will be evaluated following AFL-assisted cisplatin+5-FU treatment. The unspecific inclusion of “up to” 12 patients reflects the explorative nature of this tolerability study. Should fewer patients per group provide adequate data on LRSs associated with the treatment (for example if all patients demonstrate severe LSRs), the inclusion of 12 patients will not be performed in order to spare them potential discomfort.

Recruitment will be performed by physicians at the dermatological department, Bispebjerg Hospital and by private practice dermatologists in the Copenhagen area. Procedures for informed consent are included in Bilag 2-4.

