6.1 Primary Outcome

Tolerability measured as:

I) Local Skin Reactions (LSRs)

Non-blinded, clinical evaluation of erythema, edema, flaking, crusting/scabbing and pustulation in treated areas will be performed by a physician using a FDA-approved 0-4 point LSR scale at Days 1, 5, 14 and 30 after AFL exposure (Appendix 1). Standardized,

clinical photographs are taken to document LSRs at each visit.

II) Side Effects

Non-blinded, clinical evaluation of prolonged erythema or edema, hyper- or hypopigmentation, scarring and infection will be evaluated up to 3 months after initial AFL treatment.

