6.3 Methods for Outcome Assessment

6.3.1 Clinical Evaluation and Digital Photography

Clinical evaluation of LSRs (erythema, edema, flaking, crusting/scabbing and pustulation) in treated areas will be performed by a non-blinded physician using a FDA-approved LSR scale at Days 1, 5, 14 and 30 after baseline. The scale assesses severity of individual LSR parameters on a 0-4 points scale: none, mild, moderate, severe. Tumor size (mm) and clearance (yes or no) will also be evaluated by standard clinical dermoscopy at Day 30 and Month 3 (Appendix 1). Digital photography using a Canon Camera will be performed prior to, during, after treatment, and at control visits under standardized conditions. All images are assigned an ID-number and anonymized.

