9.1 Sample size

The primary objective of this explorative trial is to investigate tolerability of AFL-assisted cisplatin+5-FU to ensure that intolerable/severe or serious related adverse events remain minimal for the observed efficacy. While no formal statistical calculation has been performed, 12 superficial and 12 nodular BCCs in 24 subjects are considered sufficient to estimate benefit/risk of the treatment.

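### Section 9.3 plans no count of patients by skin-reaction grade or worst grade, and its medians and quartiles can leave two top-grade scores in a group of 12 unseen at a visit

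*Combined protocol and SAP*

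**What the plan says.** - **Section 9.3 (Statistics)** covers LSR scores, tumour size and clearance together, by parametric or non-parametric methods. Its one sentence on description reads "Descriptive data will be presented with medians and interquartile ranges (IQR) or means and standard deviations". It adds a Wilcoxon matched-pairs test, worded as a comparison of test areas at different times, and names SPSS 24.
- **Section 9.1 (Sample size)** makes tolerability the primary objective, "to ensure that intolerable/severe or serious related adverse events remain minimal for the observed efficacy". On size it says "While no formal statistical calculation has been performed, 12 superficial and 12 nodular BCCs in 24 subjects are considered sufficient".
- **Section 3.4 (Outcome Measures)** gives the first primary measure as "Severity and duration of clinical local skin reactions including erythema, edema, scabbing, flaking and pustulation". Section 6.1 sets the assessments: "FDA-approved 0-4 point LSR scale at Days 1, 5, 14 and 30 after AFL exposure". Section 6.3.1 describes the grading: "The scale assesses severity of individual LSR parameters on a 0-4 points scale: none, mild, moderate, severe".
- **Section 4 (Participants)** states "Up to 12 patients with superficial BCC and 12 patients with nodular BCC will be evaluated". It allows recruitment to stop short of 12 if fewer patients are informative; its example is that every patient has a severe LSR.
- **Section 8.2** directs that reactions on the grading scale are recorded as LSRs rather than adverse events, including those that need treatment.

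No section, and nothing in Appendix 1, plans the number of patients at each LSR grade, each patient's worst grade, or the number ever severe.

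**The concern.** Whether a treatment is tolerable depends on how many patients have a bad reaction, which is a question about the upper tail of the scores, counted in patients. The example in section 4 reasons in the same way. Medians and quartiles are built to resist the tail. Means and SDs on a short ordinal scale mix the tail with everything else. Visit-by-visit summaries do not link a patient's scores, so they cannot show how many patients were ever at the worst grade.

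This matters more here because of section 8.2. A severe reaction on the scale will not enter the adverse event tables, and the second primary measure (side effects) records occurrence, not LSR grade. If the LSR summary does not show the reaction, no other planned summary shows its grade. A reader of the primary result could then see a moderate median with no spread while some patients had the top grade.

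**Working it through.** The plan has no calculation to reproduce beyond 12 + 12 = 24.

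**Inputs.** Group size 12, or 24 pooled (sections 4 and 9.1). Four post-treatment assessments, Days 1, 5, 14 and 30 (section 6.1). Scores 0-4, each sign graded separately (section 6.3.1). Assumptions: all patients are assessed, summaries are made per visit, and quartiles follow the weighted-average rule, position p(n + 1), taken as the likely SPSS rule.

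**Step 1: quartiles at one visit, n = 12.**
- Q1 position: 0.25 × 13 = 3.25, so it uses ranks 3 and 4.
- Median position: 0.50 × 13 = 6.5, so it uses ranks 6 and 7.
- Q3 position: 0.75 × 13 = 9.75, so it uses ranks 9 and 10.

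Ranks 11 and 12 enter none of these. Two of 12 patients (16.7%) can have the top grade with no effect on the median or IQR. Example: ten patients at grade 2 and two at grade 4 give median 2 and IQR 2-2, the same as twelve at grade 2. A third top score reaches rank 10 and moves Q3: nine patients at 1 and three at 4 give Q3 = 1 + 0.75 × (4 − 1) = 3.25.

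**Step 2: pooled, n = 24.** Q3 position is 0.75 × 25 = 18.75 (ranks 18 and 19). Ranks 20 to 24 are free, so 5 of 24 (20.8%) can be at the top grade unseen.

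**Step 3: other quartile rules.** Of ten definitions tried, including Tukey hinges, seven give a maximum of 2 of 12 and 5 of 24; the other three give 3 and 6.

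**Step 4: mean and SD.** SD = √[(Σx² − (Σx)²/n)/(n − 1)].
- Ten at 1 and two at 3: Σx = 16, Σx² = 28, mean 1.33, SD 0.78.
- Two at 0, four at 1 and six at 2: Σx = 16, Σx² = 28, mean 1.33, SD 0.78.

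Only the first set contains a 3. Likewise, ten at 1 and two at 4, and four at 0, six at 2 and two at 3, both have Σx = 18 and Σx² = 42, so both give mean 1.50 and SD 1.17. Mean and SD respond to the tail (in the Step 1 example the mean goes from 2.00 to 2.33 and the SD from 0 to 0.78), but they do not reveal whether a top grade occurred.

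**Step 5: across visits.** With two top scores at each of four visits, the number of patients ever affected is 2 if they are the same patients throughout, and at most 2 × 4 = 8 of 12 (67%) if they are different each time. Pooled, the range is 5 to 5 × 4 = 20 of 24. The medians and IQRs are identical in every case.

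**Step 6: what counts would show.** Exact 95% intervals: 2/12 = 16.7% (2.1% to 48.4%); 8/12 = 66.7% (34.9% to 90.1%); 0/12 has an upper limit of 26.5%, and 0/24 one of 14.2%.

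**The case against.** The strongest reply is that section 9.3 is generic wording, not a closed list. The same paragraph covers clearance, which is a yes/no outcome and cannot be reported by a median, so counts are not excluded. The trial is exploratory and uncontrolled, with no formal sample size. Grades are recorded at every visit, so a table of counts can be made at reporting. No estimate is biased and no data are lost. All of this stands, and it limits the point to what is not prespecified. It does not remove the point: in an unblinded single-arm trial, the main summary of the primary outcome should be fixed before the scores are seen.

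Several stronger readings are tempting, and the documents do not support them:

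- **That section 9.1 itself requires severe LSRs to be rare.** It speaks of adverse events, and section 8.2 says scaled LSRs are not reported as such. The link runs through tolerability as the objective, LSRs as one of its measures, and the example in section 4.
- **That testing change over time is a foregone conclusion because reactions are expected in 94-100% of patients.** In section 7.2 that range is for mild to moderate erythema only. Edema is given as 33-99% and scabbing as 50-95%; flaking and pustulation have no figure. Nor is the Wilcoxon sentence plainly about change over time.
- **That 8 of 12 is a likely result.** It needs new patients at each visit, including Day 30, whereas section 7.2 expects healing by about then.
- **That mean and SD leave no trace.** They move; they are merely uninterpretable as to the top grade.

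**Conclusion.** The point holds as a gap in prespecification of the primary severity summary. Section 9.3 names only median/IQR or mean/SD for description, and nothing in the plan commits to showing how many patients reached each grade.

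The firm figure is 2 of 12 at one visit, for one sign in one group, or 5 of 24 if pooled. It assumes complete assessment of the full group and the weighted-average quartile rule; some other rules allow one more. With a smaller group it changes: for 8 patients, Q3 sits at 0.75 × 9 = 6.75 and one top score is hidden. The 8 of 12 figure is an arithmetic ceiling. That summaries are made per visit is inferred from the schedule and the Wilcoxon sentence; the descriptive sentence does not say so.

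No one should infer that the objective cannot be answered from this trial: the data will be there. Nor can grade 4 simply be read as severe. Section 6.3.1 gives four labels for five scores, so severe could be 3, 4 or both, and the calculation above refers to the top grade, not to a defined severe category.

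**What to change.** In section 9.3, specify the main LSR severity summary as follows:

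1. For each sign and by BCC subtype, the number and percentage of treated patients at each grade on Days 1, 5, 14 and 30, with the number assessed.
2. For each sign and by subtype, the distribution of each patient's worst grade over Days 1-30.
3. Median/IQR as a secondary summary; no mean/SD for LSR scores.
4. A statement that Wilcoxon p-values are not evidence of tolerability.

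In section 6.3.1, reconcile the four labels with the 0-4 scale, so that severe is defined before anyone is counted.

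The change is to wording only and uses the same visits and scores. The cost is longer tables, with five signs in two groups. Worst grade does not describe duration, the other half of the LSR outcome; the counts by visit show it only coarsely, and a duration summary would have to be specified separately.

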10.1 Quality Control

The declaration of Helsinki II will be respected as well as the standards of good clinical research. Respect for privacy as well as physically and mentally integrity of the participants will be maintained. The study will be performed in accordance with ICH GCP Guidelines and Danish Health care authorities. It will be registered to The National Committee on Health Research Ethics, Danish Health and Medicine Authority, The Danish Data Protection Agency and www.clinicaltrials.gov. Study conduction and reports are in accordance with GCP CPMP/ICH/135/95 and European Medicines Agency directive 2001/83/EC.

10.2 Data Protection and Storage

Information on previous investigations and treatments pertaining to the BCC tumor (up to 4 months from inclusion) will be accessed through the patient medical records to ensure tumors are histologically-verified and have not previously been treated.

Research using the Capital Region of Denmark's data is considered to be public research. Use and distribution of data collected in this study including photographs and biopsies, will be discussed with patients during the consent process. The project will be reported to the Danish Data Protection Agency ("Datatilsynet"). Lists of screened and participating patients including names, study ID number and date of birth will be devised. All data collected will be anonymized and protected by the Danish law regarding management of personal information and "Sundhedsloven". Data will be registered and stored for 5 years (with the exception of the biobank) after study termination at the department of dermatology, Bispebjerg Hospital. Access, monitoring and inspection of source data and study records will be permitted to the Danish Health Ministries and the GCP unit at Bispebjerg Hospital.

10.3 Source Data

A list describing source data locations (i.e. relevant medical journal descriptions from the public/private sector, pathology results) will be devised prior to initiation of the study.

10.4 Biobank

In the preliminary study, one 4 mm punch biopsy taken from the treated skin area and one 5ml blood sample per patient will confirm adequate local drug uptake and limited systemic permeation. Biopsies and blood samples are sent for analysis by collaborators at Copenhagen University. No extra material will be taken. Any remaining biological material will be returned to primary investigator [name], Bispebjerg Hospital at the end of the study for potential use in future investigations. The material will be handled confidentially and will not be used in other scientific studies without Videnskabsetisk Komite's permission. Prior to storage, permission will be sought from Datatilsynet as well as patients. The biobank expires September 1, 2019 whereafter the material is kept for 10 years for future research and thereafter be destroyed.

11. Ethics

No previous trials have investigated AFL-assisted cisplatin+5-FU as a topical treatment in patients. Based on our preclinical results, we expect to successfully treat study participant's BCCs. During the trial, individual participants will be followed closely by treating phycisians. In the event of side

effects, these will be managed according to guidelines by investigating physicians. In the event of an unsuccessful treatment outcome, histological assessment should detect residual tumor tissue at 3 months control—a duration which is in accordance with general guidelines for established non-surgical BCC treatments. Patients will receive conventional therapy to ensure complete tumor removal. Beyond removal of the tumor, patients are not anticipated to benefit from the study.

While cisplatin and 5-FU are chemotherapeutics, side effect profiles associated with IV therapy (i.v. doses: 100 mg/m² (cisplatin); 400-600 mg/m² (5-FU)) cannot be transferred to the topical administration route used here. We do not anticipate systemic drug exposure due to the applied ultralow drug doses and small treatment surface areas. On the other hand, notable local erythema/edema, flaking/scaling, crusting, and erosion/ulceration are anticipated and represent, in addition to the inconvenience of multiple visits to the Hospital as well as invasive biological sampling, drawbacks of study participation. Still, as with standard 4 week topical 5-FU treatment, we expect local skin reactions to be tolerable and heal without sequelae.

On a broader socioeconomic scale, the study may have an impact on future BCC treatment, a cancer form that each year affects more people than breast-, prostate-, lung- and colon cancer combined. Skin cancer represents a massive and ever-expanding health concern, and the demand for more gentle treatments particularly in aging, sun-damaged or immuno-suppressed populations is increasing. We expect that developing a new, minimally-invasive topical treatment would be beneficial to the tens of millions of patients who yearly receive a BCC diagnosis. These benefits include the option of forgoing surgery and associated complications, in favor of a more gentle and repeatable treatment that would ensure preservation of function and appearance of vital anatomical structures. Importantly, the laser technology used in this project is commonly available and has previously led to improved treatments for precancerous lesions that have now been implemented at our facility. Both investigated drugs are now produced cheaply and generically. The treatment is therefore not expected to pose an insurmountable healthcare cost should it be implemented. It is thus determined that the knowledge gained in this study outweigh the disadvantages and side effects that patients may experience as a result of their participation.

12. Financial Considerations and Insurance

[name] [name] is initiator of the study and carries chief responsibility for the trial. Primary investigator is PhD student [name]. Internal funds at Dermatology Department Bispebjerg Hospital and research grants awarded to [name] and [name] will cover project-related costs, including reimbursement for study materials. All funding will be disbursed to relevant project accounts at Bispebjerg Hospital. No personal honoraria are awarded to investigators or participants. None of the collaborators have any personal relation or economic stake in the laser technology used in this trial. Treatments are performed at Dermatology Department Bispebjerg Hospital and patients are covered under the Hospital's patient insurance.

13. Information to Participants

After recruitment at the dermatological department, Bispebjerg Hospital or via private practice dermatologists, participants will be asked to provide informed consent at a prescheduled screening visit (Section 5). Investigators ([name], [name], [name]) are responsible for giving clear verbal and written information about aims, design and risks of the study, as stated in "*Information og samtykke til deltagelse i sundhedsvidenskabelige forskningsprojekter*" by "Sundheds- og Ældreministriet". In a private setting undisturbed and not in use by others, the participant will be made aware of their right to have an assessor present, that participation is voluntary, and that withdrawal is possible at any time during the study. Participants will be given adequate consideration time (minimum 24 hours). Participants will be asked to sign a consent form and two separate forms regarding use of clinical photos and biological material. Forms will all be stored together. A copy of the consent form will be given to participants and another copy will be stored in the study journal.

14. Publication of Results

The study will be sought published in an international dermatological journal and presented at scientific conferences, regardless of positive, negative or inconclusive results. No company has involvement or influence on publication of results or transmission of data. Authorships are given according to the Vancouver guidelines.

References:

1. Stern RS. Prevalence of a history of skin cancer in 2007: results of an incidence-based model. *Arch Dermatol.* 2010;146(3):279-82.

APPENDIX 1- OUTCOME MEASURES AND TECHNIQUES

Outcome measures	Techniques
LSR (Primary outcome) Days 1-30	CLINICAL ASSESSMENT 
• FDA-accepted 0-4 point LSR scale
Side Effects (Primary outcome) Up to 3 months	CLINICAL ASSESSMENT 
• Prolonged erythema• Prolonged edema• Infection• Hyperpigmentation• Hypopigmentation• Scarring
Tumor size (mm) and clearance (Secondary outcome) Baseline, Day 30 (not RCM) and at Month 3	
• Clinical evaluation• Dermoscopy• OCT (Vivosight)• HIFU (Logiq P9)• RCM (Vivascope)• Histology
